## 7.2. Safety Assessments

Safety assessments will include collection of AEs, Serious Adverse Events (SAEs), vital signs, physical examination, electrocardiogram (ECG, 12-lead), and laboratory assessments (including pregnancy tests). Further details of these assessments are described in the [Schedule of Activities](#) table.

### 7.2.1. Pregnancy Testing

For female patients of childbearing potential, a serum or urine pregnancy test, with sensitivity of at least 25 mIU/mL human chorionic gonadotropin (hCG) and assayed in a certified laboratory, will be performed on 2 occasions prior to starting study treatment - once at the start of screening and once at Day 1 of the Lead-in Phase, immediately before administration of avelumab/placebo. Following a negative pregnancy test result at screening, appropriate contraception must be commenced and another negative pregnancy result will then be required at Day 1 of the Lead-in Phase visit before the patient may receive the study treatment. Pregnancy tests (serum or urine) will also be routinely repeated as described in the [Schedule of Activities](#) prior to each dose of study treatment during the active treatment period, at the End of Treatment visit, during the post-treatment safety follow-up visits up to at least 30 days after the last study treatment infusion, and additionally whenever 1 menstrual cycle is missed or when potential pregnancy is otherwise suspected. In the case of a positive confirmed pregnancy, the patient will be withdrawn from administration of study treatment but may remain in the study.

Additional pregnancy tests may also be undertaken if requested by institutional review boards (IRBs)/ethics committees (EC) or if required by local regulations.

### **7.2.2. Adverse Events**

Assessment of adverse events will include the type and severity (graded by NCI CTCAE version 4.03), timing, seriousness, and relatedness. Adverse events that occur during the study will be recorded on the adverse events CRF page.

Baseline signs and symptoms should be recorded in the medical history CRF page.

### **7.2.3. Laboratory Safety Assessments**

Hematology, blood chemistry, and urinalysis will be collected at the time points described in the [Schedule of Activities](#) and analyzed at local laboratories. They may also be performed when clinically indicated. Abnormal laboratory test results should be repeated as soon as possible (preferably within 24-48 hours). The required laboratory tests are listed in [Table 12](#).

**Table 12. Required Laboratory Tests**

Hematology	Chemistry Panel (*denotes core chemistry test)	Urinalysis	Coagulation Tests	Pregnancy Tests
Hemoglobin	ALT*	Protein, glucose, blood	PT or INR	For female patients of childbearing potential, serum or urine
Platelets	AST*		aPTT	
WBC	Alkaline Phosphatase*			
Absolute Neutrophils	Sodium*			
Absolute Lymphocytes	Potassium*			
Absolute Monocytes	Magnesium*			
Absolute Eosinophils	Chloride*			
Absolute Basophils	Total Calcium*			
	Total Bilirubin* °			
	BUN or Urea*			
	Creatinine*			
	Glucose*			
	Phosphorus or Phosphate*			
	Albumin*			
	Total Protein*			
	Uric Acid			
	Amylase			
	Gamma glutamyl transferase (GGT)			
	Cholesterol			
	Creatine kinase			
	C-reactive protein (CRP)			
	Lactate dehydrogenase (LDH)			
	Lipase			
	Triglycerides			
	HBV, HCV serology			
	Thyroid Function Tests: TSH, free T4			
	Other Tests: ACTH,			

° For potential Hy's Law cases, in addition to repeating AST and ALT, laboratory tests should include albumin, creatine kinase, total bilirubin, direct and indirect bilirubin, GGT, PT/INR, alkaline phosphatase, and acetaminophen levels.

ACTH=adrenocorticotrophic hormone, ALT=alanine aminotransferase, aPTT=activated partial thromboplastin time, AST=aspartate aminotransferase, BUN=blood urea nitrogen, CRP=C-reactive protein, GGT=gamma-glutamyltransferase, HBV=hepatitis B virus, HCV=hepatitis C virus, INR=international normalized ratio, LDH=lactate dehydrogenase, PT=prothrombin time, TSH=thyroid-stimulating hormone, WBC=white blood cell

**7.2.4. Physical Examinations and Vital Signs**

Patients will have physical examinations to include major body systems, assessment of ECOG performance status, weight and height (height will be measured at screening only) at the time points described in the [Schedule of Activities](#) table.

At baseline evaluation, nasopharyngoscopy is strongly recommended.

Weight for the purposes of dose calculation will be recorded at screening and within 3 days prior to each dose of avelumab. Baseline weight is used for the Lead-in D1 dose calculation.

Vital signs (blood pressure and pulse rate) will be also recorded as reported in the [Schedule of Activities](#) table. They should be taken before any other assessments (eg, PK, laboratory blood draws), prior to receipt of study treatment with the patient in the seated position after the patient has been sitting quietly for at least 5 minutes.

### **7.2.5. 12-Lead Electrocardiograms**

All patients require a single ECG measurement at screening and at the End-of-Treatment/Withdrawal visit or when clinically indicated. Clinically significant findings seen on ECG during the treatment period should be recorded as adverse events.

Triplicate 12-lead (with a 10-second rhythm strip) tracing will be collected in approximately 30 patients in each arm of the study. It is preferable that the machine used has a capacity to calculate the standard intervals automatically. In these patients, on-treatment triplicate ECGs will be performed on the day of avelumab/placebo administration (ie, Day 1 of the Lead-in Phase, and Days 8, 25, and 39 of the CRT Phase; if the avelumab/placebo dosing day is shifted for patient scheduling reasons, the ECG assessment should be shifted also). At each time point (see the [Schedule of Activities](#)) 3 consecutive 12-lead ECGs (triplicates) will be performed approximately 2 minutes apart to determine mean QTc (average of triplicates) prior to avelumab/placebo administration and at the end of infusion. If the mean QTc is prolonged ( $>500$  msec, ie, CTCAE Grade  $\geq 3$ ), then the ECGs should be re-evaluated by a qualified person at the site for confirmation as soon as the finding is made, including verification that the machine reading is accurate.

If a manual reading verifies a QTc of  $>500$  msec, immediate correction for reversible causes (including electrolyte abnormalities, hypoxia and concomitant medications for drugs with the potential to prolong the QTc interval) should be performed. In addition, repeat ECGs should be immediately performed hourly for at least 3 hours until the QTc interval falls below 500 msec. If QTc interval reverts to less than 500 msec, and in the judgment of the investigator(s) and sponsor is determined to be due to cause(s) other than investigational product, treatment may be continued with regular ECG monitoring as clinically indicated. If in that timeframe the QTc intervals rise above 500 msec the investigational product will be held until the QTc interval decreases to  $\leq 500$  msec. Patients will then restart the investigational product at the next lowest dose level or have their dosing delayed as appropriate for specific investigational product. If the QTc interval has still not decreased to  $<500$  msec after 2-weeks, or if at any time a patient has a QTc interval  $>515$  msec or becomes symptomatic, the patient will be removed from the study. Additional triplicate ECGs may be performed as clinically indicated.

Prior to concluding that an episode of prolongation of the QTc interval is due to investigational product, thorough consideration should be given to potential precipitating factors (eg, change in patient clinical condition, effect of concurrent medication, electrolyte disturbance) and possible evaluation by a specialist.

If a patient experiences any cardiac or neurologic AEs (especially syncope, dizziness, seizures, or stroke), an ECG in triplicate should be obtained at the time of the event.

When matched with PK sampling, the ECG must be carried out before each PK sample drawing such that the PK sample is collected at the nominal time (ie, the timing of the PK collections over rides the timing of the ECG collections).

Clinically significant findings seen on ECGs during the treatment period should be recorded as AEs.

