**Table 3. SCHEDULE OF ACTIVITIES – Maintenance Phase, End of Treatment/Withdrawal, and Short-/Long-Term Follow-up Periods**

Visit Identifiers 	-- Study Treatment --		----- Post-Treatment -----			
	Maintenance Phase* (1 cycle = 4 weeks)		End of Treatment (EOT)/ Withdrawal (+3 days) 	Follow-up 		
	Day 1 (±3 days)	Day 15 (±3 days)		Short-Term (after last dose or EOT/Withdrawal Visit)		Long-Term (+ 14 days)
				30 days (±3 days)	90 days Follow-up Telephone Contact* (±3 days)	
Documentation						
Physical Examination 	X		X			
Contraception Check	X		X	X		
ECOG Performance Status	X		X	X		
Vital Signs 	X	X	X			
Laboratory Studies						
Hematology & Blood Chemistry 	X	X	X	X		
Coagulation 	If clinically indicated		X	If clinically indicated		
Thyroid Function Tests and ACTH 	X (then Q8W)		X	X		
Pregnancy Test 	X	X	X	X		
Urinalysis 	If clinically indicated		X	If clinically indicated		
12-lead ECG 	If clinically indicated		X			
Disease Assessments						
Tumor Assessments (including scans) 	X (12 weeks after completion of CRT, then Q16W for 48 months, then Q24W until PD per modified RECIST v1.1; additional assessment to be performed at the EOT/Withdrawal Visit)					
Other Clinical Assessments						
Adverse Events 	X	X	X	X		
Concomitant Medications/Treatments 	X	X	X	X		
Initiation of New Systemic Anticancer Treatment			X	X	X	X
Survival Assessment 						X

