All patients will be followed for survival until death, end of the study, or patient withdrawal of consent, whichever comes first, regardless of initiation of new cancer therapy. All patients will be followed for safety with evaluations through 90 days after the last study treatment administration or until the time of initiation of new systemic anticancer treatment. The Day 90 Short-Term Follow-up Visit will be conducted as a phone call. If any concern arises, the patient will be called in for a follow-up visit within 5 calendar days of the initial phone call for appropriate assessment (as per the investigator’s medical judgement). Beyond the Day 90 Short-Term Follow-up Visit, all patients will be followed every 16 weeks (Q16W) for survival and new systemic anticancer treatment within the long-term follow-up period.

Patients who refuse to return to the site for evaluations should be contacted by telephone as an alternative.

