- If a patient withdraws from study treatment for a reason other than disease progression per modified RECIST v1.1, radiological tumor assessments are to continue until disease progression per modified RECIST v1.1 even if a new anti-cancer therapy is initiated.

- A head and neck CT or MRI, chest CT, and PET scan are required at baseline and at 12 weeks after completion of CRT. High resolution PET/CT does not require additional CT thorax/neck/brain. MRI brain may be performed if clinically indicated. Subsequent PET scans may be performed during the Maintenance Phase in the absence of clinical or CT complete resolution of nodal disease (described in [Section 3.3](#)) or at the investigator's discretion. Baseline tumor assessments should be done within 28 days prior to randomization.

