### **6.4. Patient Withdrawal**

Patients may withdraw from the study at any time at their own request, or they may be withdrawn at the discretion of the investigator or sponsor for safety or behavioral reasons, or the inability of the patient to comply with the protocol-required schedule of study visits or procedures at a given study site.

Reasons for withdrawal of study treatment may include:

- Disease progression per modified RECIST v1.1;
- Global deterioration of health status requiring discontinuation;
- Unacceptable toxicity. If the unacceptable toxicity is clearly attributed to one of the investigational products, then withdrawal from study treatment may be considered, dependent upon the treatment and specific toxicity. If a patient cannot tolerate cisplatin, or has a toxicity-related treatment delay due to the radiation therapy, withdrawal from this study is neither required nor suggested;
- Pregnancy;
- Significant protocol violation (including radiation therapy protocol violations);
- Lost to follow-up;
- Patient refused further treatment;
- Study terminated by sponsor;
- Death.

Reasons for withdrawal from study follow-up may include:

- Study terminated by the Sponsor;
- Lost to follow-up;
- Refused further follow-up;
- Death.

If a patient does not return for a scheduled visit, every effort should be made to contact the patient. All attempts to contact the patient and information received during contact attempts must be documented in the patient's medical record. In any circumstance, every effort should be made to document patient outcome, if possible. The investigator should inquire about the reason for withdrawal, request that the patient return for a final visit, if applicable, and follow-up with the patient regarding any unresolved AEs.

If the patient refuses further visits, the patient should continue to be followed for survival unless the patient withdraws consent for disclosure of future information or for further contact. In this case, no further study specific evaluations should be performed, and no additional data should be collected. The sponsor may retain and continue to use any data collected before such withdrawal of consent.

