### 7.8. Tumor Response Assessment

Tumor assessments will include all known or suspected disease sites. Imaging at screening (baseline) and at 12 weeks after completion of CRT must include a head and neck CT or MRI, chest CT, and PET scan. High resolution PET/CT does not require additional CT thorax/neck/brain. MRI brain may be performed if clinically indicated. Other areas may be scanned as clinically indicated. The CT and MRI scans should be performed with contrast agents unless contraindicated for medical reasons. The same imaging technique used to characterize each identified and reported lesion at baseline will be employed in the following tumor assessments. At a minimum, the CT modality used at baseline will be the expected imaging technique for follow-up. Any clinical progression concern warranting a biopsy must have supporting imaging (ie, CT, MRI, PET, or digital photograph) archived for documentation purposes. Additional imaging modalities may also be employed if clinically required. Baseline tumor assessments should be done within 28 days prior to randomization.

Radiographic and clinical evaluations will be conducted with the same schedule in both treatment arms of the study. The investigator will assess antitumor activity based on radiological assessments and clinical evaluation of patients using modified RECIST v1.1 ([Appendix 3](#)) at screening (baseline), 12 weeks after the completion of CRT, every 16 weeks thereafter for 48 months (208 weeks), and every 24 weeks (Q24W) thereafter until confirmed disease progression per modified RECIST v1.1 and regardless of discontinuation of study treatment or initiation of subsequent anti-cancer therapy.

The assessment performed 12 weeks after completion of the CRT is to include CT and PET for all patients and MRI also if clinically appropriate in patients who did not achieve clinical or CT/MRI-based radiological nodal CR at the tumor assessment performed 12 weeks following completion of CRT, and follow-up PET scans are recommend every 4 months (16 weeks) with the CT imaging for 24 months (104 weeks), then every 6 months (Q24W) in Years 3-5. CT imaging should be obtained as described in the [Schedule of Activities](#) beyond Year 5. The time window for tumor assessments is  $\pm 1$  week except for the assessment at Week 12 which cannot be done earlier but can be done up to one week later.

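### The QTc rule in Protocol 7.2.5 removes patients from the study, which read literally conflicts with the follow-up required by Sections 3.1, 3.2 and 7.8

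*Protocol*

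**What the plan says.** Protocol 7.2.5 sets out steps for a confirmed QTc above 500 msec: correct reversible causes, repeat the ECG, hold the investigational product, then restart or delay it. The last step covers three cases: QTc not below 500 msec after two weeks, QTc above 515 msec at any time, or a patient who becomes symptomatic. In each case "the patient will be removed from the study".

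The follow-up rules elsewhere in the protocol are:

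- Section 3.1 (text below Table 4): "All patients will be followed for survival until death, end of the study, or patient withdrawal of consent".
- Section 3.2: "If a patient withdraws from study treatment for a reason other than disease progression per modified RECIST v1.1, radiological tumor assessments are to continue", and they run until progression.
- Section 7.8: assessments run "until confirmed disease progression per modified RECIST v1.1 and regardless of discontinuation of study treatment".
- Section 6.4: the investigator or sponsor may, at their discretion, withdraw a patient from the study for safety. Unacceptable toxicity is listed among reasons for stopping treatment. The examples of reasons for leaving follow-up are sponsor termination, loss to follow-up, refusal and death. For a patient who declines visits the section says: "If the patient refuses further visits, the patient should continue to be followed for survival", unless consent to disclosure or contact is withdrawn.
- Section 7.2.1, on pregnancy, separates treatment from study: "the patient will be withdrawn from administration of study treatment but may remain in the study". Section 5.2 does the same after unblinding, sending the patient to the post-treatment procedures.

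**The concern.** A site cannot both remove a patient from the study and keep following that patient. Section 7.2.5 requires the first; Sections 3.1, 3.2 and 7.8 require the second. Because the protocol elsewhere distinguishes leaving treatment from leaving the study, a coordinator has some reason to take 7.2.5 at its word.

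What is at stake is avoidable loss of outcome data in an analysis of all randomized patients. The loss would be triggered by a toxicity rather than by the end of follow-up, so the censoring could be related to prognosis. It would also be recorded as compliance with the protocol, not as a deviation, and so would be hard to spot later.

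**Working it through.** The question is one of text, and the plan states no figure to reproduce.

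**1. Does 7.2.5 fall within the scope of the other rules?**

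- *Section 3.1* covers all patients and names three stopping points: death, end of study and withdrawal of consent. A QTc value is none of these.
- *Section 3.2* applies when treatment stops for a reason other than progression. A patient removed from the study necessarily stops treatment, and QTc prolongation is not progression, so the condition is met.
- *Section 7.8* applies regardless of why treatment stopped.
- *Section 6.4* permits safety withdrawal from the study but does not require it. A discretion does not explain an automatic rule.

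On the literal reading the conflict is therefore with all three follow-up rules. If 7.2.5 means removal from treatment, it conflicts with none of them.

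**2. What would the analysis do with a removed patient?**

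Under SAP 6.1.1.1, Table 9, a patient without progression or death is censored at the last adequate tumor assessment or clinical evaluation documenting no progression. With no such post-baseline record and no death, censoring is at randomization. Under SAP 6.2.2.1, OS is censored at last contact.

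Timing, in nominal days: the scheduled on-treatment triplicate ECGs fall on Lead-in Day 1 and CRT Days 8, 25 and 39. The latest removal under the two-week trigger from a scheduled ECG is about CRT Day 39 + 14 = Day 53. The first scheduled post-baseline tumor assessment is 12 weeks after completing 7 weeks of radiotherapy, at about Day 49 + 84 = Day 133. A removal triggered by a scheduled ECG would thus precede the first scheduled post-baseline scan. PFS would then rest on any clinical evaluation or unscheduled scan on record.

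**3. How many patients?**

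- Scheduled on-treatment triplicate ECGs: about 30 per arm, so 2 × 30 = 60, and 60/640 = 9.4%.
- This is not a ceiling. Section 7.2.5 also calls for triplicate ECGs after any cardiac or neurologic adverse event, clinically indicated ECGs at any time, and an end-of-treatment ECG for everyone.
- Neither document gives a rate at which the QTc thresholds are crossed, so the number removed cannot be calculated.
- Illustration only, assuming 1 to 6 removals (6 is 10% of the 60) and the planned event fraction of 289/640 per patient: 1 × 289/640 = 0.5 to 6 × 289/640 = 2.7 expected PFS events unobserved. The PFS analysis is event-driven, so the practical result would be a slightly later cutoff.

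**The case against.** **The intent is plain.** The preceding steps of the rule concern dosing, and the protocol uses study-withdrawal language loosely elsewhere. The toxicity bullet in Section 6.4 sits under reasons for stopping treatment, yet says "withdrawal from this study is neither required nor suggested". This stands as evidence of intent. It does not tell a site which sense applies in 7.2.5, where the wording is mandatory.

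**The list in 3.1 is not exhaustive.** Section 6.4 adds loss to follow-up and discretionary safety withdrawal, so 7.2.5 might be a pre-specified case of the latter. The first part is correct: 3.1 should not be read as a closed list. The second would need 7.2.5 or 6.4 to say so, and neither does. The follow-up exits in 6.4 are only examples, so the absence of toxicity there is suggestive, not conclusive.

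**Other text limits the damage.** Schedule of Activities Table 3, footnotes 3 and 14, repeat survival follow-up for all patients, and Section 6.4 asks for every effort to document outcome. The SAP counts progression or death as an event despite earlier missed assessments. These help only if the site keeps collecting data, which is what the literal wording would end.

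**A stronger reading to avoid.** A reader might infer where censoring would fall by assuming an exit scan whenever the last one is more than six weeks old, since Table 3 calls for an "additional assessment to be performed at the EOT/Withdrawal Visit". The documents do not support that. Footnote 2 goes on to confine early-withdrawal imaging to patients who discontinue early and refuse follow-up, and a patient removed under the QTc rule has not refused. Whether an exit scan would be done is unsettled, so nothing here depends on one.

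**Conclusion.** The point holds as a narrow conflict of rules. Taken literally, 7.2.5 ends follow-up that 3.1, 3.2 and 7.8 require, and 6.4's discretionary safety withdrawal does not reconcile them. The likely intent is withdrawal from treatment, in which case only the wording is wrong.

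The conclusion rests on one assumption: that at least some sites would act on the words as written. The size is unknown for want of a QTc event rate, and probably small.

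A reader might infer bias in the hazard ratio or a material loss of power. The documents support neither: they give no rate, no reason to expect different rates by arm, and an event-driven analysis. No effect on the primary result is claimed. No other part of 7.2.5 is challenged. This is a minor wording correction worth making because it is nearly free.

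**What to change.** In Protocol 7.2.5, replace the closing phrase with:

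*the patient will be permanently discontinued from the study treatment(s) concerned [sponsor to name avelumab/placebo and/or cisplatin; IMRT per investigator judgment] but will remain in the study for tumor assessments and survival follow-up per Sections 3.1, 3.2 and 7.8.*

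The treatment should be named. Section 5 counts avelumab/placebo, cisplatin and IMRT all as study treatments, so an unqualified reference could be read as stopping curative-intent chemoradiotherapy. The model is the pregnancy rule in Section 7.2.1, with *will remain* in place of its permissive wording, because the follow-up rules leave no option.

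The cost is one phrase at the next protocol amendment. It adds no visits or data collection beyond the Schedule of Activities, and the SAP needs no change.
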